Cardiovascular: angina pectoris (1% to 5%), bradycardia (1% to 5%), chest pain (1% to 5%), hypertension (1% to 5%), hypotension (1% to 5%)

Central nervous system: Anxiety (1% to 5%), depression (1% to 5%), headache (1% to 5%), pain (1% to 5%)

Dermatological: hyperpigmentation of eyelashes, increased growth of eyelashes

Endocrine and metabolic: hypercholesterolemia (1% to 5%)

Gastrointestinal: dyspepsia (1% to 5%), gastrointestinal disorders (1% to 5%)

Genitourinary: prostate disease (1% to 5%), urinary incontinence (1% to 5%), urinary tract infection (1% to 5%)

Hypersensitivity: Hypersensitivity Reactions (1% to 5%)

Infection: Infection (1% to 5%)

Neuromuscular and skeletal: arthritis (1% to 5%), back pain (1% to 5%)

Respiratory: Bronchitis (1% to 5%), flu-like symptoms (1% to 5%), sinusitis (1% to 5%)

Post-marketing and / or case reports :

Asthma, tachycardia

vi. Contraindications

Allergy to prostaglandin analogues or any of the other ingredients of the product

Being pregnant or considering pregnancy (Risk Factor C for pregnancy)

vii. Interactions

Non-steroidal anti-inflammatory drug: may increase the therapeutic efficacy of prostaglandins

viii. Pharmacodynamics and pharmacokinetics

Start of action: 2 hours

Maximum effect: 12 hours

Half life: 45 minutes

ix. Inactivation and elimination

Inactivation by the kidneys, liver and lungs.

4. Study population

a. Target population:

All adult patients with primary open angle glaucoma, normotensive glaucoma, or ocular hypertension requiring pharmacological treatment seen at CHUS.

5. Sample size and inclusion / exclusion criteria

The calculation of the sample size is based on a paired t test, assuming a normal distribution of intraocular pressure. To demonstrate an equivalence between Travoprost original (Travatan Z) and generic Travoprost, a sample size of 69 patients will be required. This will detect a difference of 1.5mmHg with a power of 80% and an alpha of 0.05, assuming a standard deviation of 3.5mmHg. Assuming a loss at follow-up of 10%, the required number of patients is 76.

a. Inclusion criteria

- To be of age
- Be able to consent and sign the consent form
- Have a diagnosis of primary open angle glaucoma, normotensive glaucoma, or ocular hypertension requiring pharmacological treatment

b. Exclusion criteria

- Angle closure glaucoma
- Having had laser iridotomy
- Allergy known to Travatan or Travaprost, or to any other components of the products

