
Group 4 (Patient already randomized to receive generic Travoprost first)
	
 • Presentation of the study to the patient • Obtaining consent • A bottle of generic Travoprost given with instruction to instill a drop at bedtime in the eye reaches 	
 • IOP taken by the resident • Complete the questionnaire on the comfort of the treatment • A bottle of Travoprost original (Travatan Z) given with instructions to instill a drop at bedtime in the eye reaches 	
 • IOP taken by the resident • Complete the questionnaire on the comfort of the treatment • End of the study

9. Data analysis

The database will be created with Microsoft Excel.

Statistical calculations will be done with SPSS v20.

a. Comparison of the composition of the different groups

A t-test will be used for continuous variables (if the data are not normally distributed, a Mann-Whitney test will be used).

A Chi-square test will be used for categorical variables (if the frequency is less than 5 for a variable, an exact Fisher test will be used).

b. Comparison of groups at the end of the study

A paired t test will be used if the data is normally distributed (otherwise, a Wilcoxon test will be used).

c. Analysis of the therapeutic effect of drugs

An ANOVA test will be used to compare the effect of the treatments over time (an appropriate transformation will be applied to the data if it is not normally distributed).

d. Comparison of adverse effects between the two treatments

A McNeman test will be used to see if each side effect is as common with both treatments.

e. Comparison of compliance with each treatment

A paired t test will be used to see if patients have the same compliance for each treatment (Wilcoxon test if non-normal data).

10. Limitations

There is a potential bias of information if a patient believes that the generic is less effective, which could lead to a decrease in compliance or a change in dosage by the patient (eg: he could put it twice a day and not once). To counter this bias, the importance of abiding by the prescribed posology will be explained to patients.

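### Sections 9b and 9c let an unspecified normality check change the IOP analysis, and the fallback branches give no mean difference in mmHg to set beside the plan's 1.5 mmHg

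*Combined protocol and SAP*

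**What the plan says.** The combined protocol and SAP touches this point in three places.

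- **Section 5 (sample size).** "The calculation of the sample size is based on a paired t test, assuming a normal distribution of intraocular pressure". The target is stated as: "This will detect a difference of 1.5mmHg with a power of 80% and an alpha of 0.05, assuming a standard deviation of 3.5mmHg". The evaluable number is 69, raised to 76 for 10% loss.
- **Section 9b (end-of-study comparison).** The rule reads: "A paired t test will be used if the data is normally distributed (otherwise, a Wilcoxon test will be used". The section does not name IOP. It is read here as the IOP comparison because section 5 sizes the trial on a paired t test of IOP.
- **Section 9c (therapeutic effect).** "An ANOVA test will be used to compare the effect of the treatments over time", with the proviso that "an appropriate transformation will be applied to the data if it is not normally distributed".

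The plan does not say which normality test is used, at what level, or whether it is applied to raw IOP or to the paired differences. It does not name the transformation. It specifies no estimate or confidence interval for any branch, and it names neither 9b nor 9c as the primary analysis.

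**The concern.** The objective is to learn whether the generic lowers IOP as well as the brand, and the design figure is a difference in mmHg. The result therefore needs to be an estimate and interval in mmHg. Under the plan, whether such a result can be produced depends on a preliminary check made on the trial's own data.

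There are two separate switches. In 9b, a failed check replaces the paired t test with a Wilcoxon test, for which only a p-value is planned. In 9c, a failed check replaces raw IOP with transformed IOP, and the effect then sits on another scale, such as a ratio after a log. In either fallback the reader has no mean mmHg difference to compare with 1.5 mmHg.

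Section 5 also places normality on IOP itself. A paired t test depends on the within-patient differences, and with about 69 pairs it needs only that their mean be roughly normal.

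**Working it through.** **Inputs from the documents.** Difference 1.5 mmHg, SD 3.5 mmHg, power 80%, alpha 0.05, 69 evaluable pairs (all section 5). The text does not say whether 3.5 is the SD of one reading or of the paired difference, or whether alpha is one- or two-sided.

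**Assumptions not in the documents.** Reading step of 0.5, 1 or 2 mmHg; a 5% Shapiro-Wilk or Lilliefors-corrected Kolmogorov-Smirnov check; the shape of any skewed distribution.

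**Step 1. Reproduce 69, to see which SD of differences is plausible.** n = ((z_alpha + z_power) × SD_diff / 1.5)².

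- SD_diff = 3.5, two-sided: (2.802 × 3.5 / 1.5)² = 42.7, so 43 (45 with the t distribution). This is not 69.
- SD_diff = 3.5 × √2 = 4.95 (zero within-patient correlation), one-sided: (2.487 × 4.95 / 1.5)² ≈ 67.3, so 68, and exactly 69 with the t distribution.
- Correlation 0.2, SD_diff = 3.5 × √1.6 = 4.43, two-sided: (2.802 × 4.43 / 1.5)² ≈ 68.4, so 69.

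The stated 69 is thus recovered only under readings that the text does not spell out. Both 3.5 and 4.95 are carried forward as SD_diff.

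**Step 2. How often rounding alone trips the check.** Truly normal readings, 69 pairs, 4,000 simulated trials per setting, check applied to the paired differences:

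| Reading step | SD_diff 3.5: Shapiro-Wilk / KS | SD_diff 4.95: Shapiro-Wilk / KS |
|---|---|---|
| none | 5% / 4% | 5% / 3% |
| 0.5 mmHg | 7% / 10% | 5% / 7% |
| 1 mmHg | 12% / 35% | 7% / 17% |
| 2 mmHg | 79% / 98% | 28% / 67% |

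The rate runs from nominal to almost certain, depending on three things that the documents leave open.

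**Step 3. What the switch in 9b does when rounding is the only cause.** 3,000 trials per setting, steps of 1 and 2 mmHg, SD_diff 3.5 and 4.43:

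- Two-sided type I error of the two-stage rule: 4.9% to 5.5%.
- Power at 1.5 mmHg: 92.7-94.0% against 93.2-94.1% for the t test at SD_diff 3.5, and 77.2-78.0% against 77.9-78.0% at 4.43.
- The t and Wilcoxon decisions differ in 1% to 5% of trials.

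**Step 4. What it does when the differences are truly skewed.** Gamma differences with mean zero and skewness 1 (assumed): the two-stage rule rejects in 10.5% of trials, against 5.1% for the t test. Simulation error is of the order of one percentage point, so read this as about 10% against about 5%. The signed-rank test no longer tests the mean once symmetry is lost.

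**Step 5. Whether the t interval needs protecting.** With rounded normal data its coverage was 94% to 96%. With exponential differences, a strong skew, it was 93.8%.

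**Step 6. The transformed branch in 9c.** Taking a log as an example, 1.5 mmHg is 1.5/12 = 12.5% at an IOP of 12 but 1.5/24 = 6.25% at 24. No single ratio corresponds to the design figure.

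**The case against.** The strongest reply is that the harm in 9b is small. Section 9b states a rule, which is narrower than free choice. If rounding is the only departure from normality, the differences stay symmetric, error rates hold, and a Hodges-Lehmann estimate would be in mmHg and target the same value as the mean. Nor does the plan specify an interval for the t-test branch, so the missing interval is a general gap and was not created by the switch. All of this stands. It confines the real damage to true skew and to the transformed ANOVA. It does not remove the defect, because the plan specifies no Hodges-Lehmann estimate and leaves the trigger of the rule undefined.

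Four stronger readings are tempting, and the documents do not support them:

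- **A three-way choice between t test, Wilcoxon and transformed ANOVA.** The ANOVA in 9c runs in any case; the check affects only its scale.
- **Whole-number tonometer readings will usually trip the check.** Section 7 names the Goldmann tonometer but gives no reading resolution, and section 9 names no normality test. High rates come from coarse steps or from an SD of differences below any that section 5 suggests.
- **Wilcoxon discards the patients who best support equivalence.** Dropping zero differences would bear on equivalence only if the test assessed equivalence. As written, both tests look for a difference. The absence of an equivalence rule is a separate matter.
- **An unmasked analyst will choose between tests.** The trial is open and the resident collects and manages the data (sections 3 and 7), but no analyst is identified.

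**Conclusion.** The point holds, at modest size. Two undefined normality checks govern the IOP analyses in 9b and 9c, and in their fallback branches the planned output cannot be set beside 1.5 mmHg. At about 69 pairs the check protects against little, since t-interval coverage stayed near 95% under rounding and at about 94% under strong skew.

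A reader might infer that rounding makes the trial's error rate wrong; the simulations show that it does not. A distorted error rate, about 10% instead of 5%, needs truly skewed differences, and the skewness of 1 used here is an assumption. The change of scale in 9c needs no such assumption beyond the check failing. This is a free improvement, not a flaw that invalidates the design.

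**What to change.** - **Sections 9b and 9c.** State that the main IOP result is the mean within-patient difference, generic minus brand, in mmHg with its t-based confidence interval, whatever a normality check shows. Preferably take it from a crossover model with a period term, since each patient receives the products in sequence. Read the interval against 1.5 mmHg.
- **Sensitivity analysis only.** Keep the Wilcoxon test with a Hodges-Lehmann interval, or a bootstrap interval, in mmHg.
- **Section 9c.** Drop the transformation as a route to the main result.
- **Section 5.** Place the normality assumption on the paired differences.

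The cost is wording in three sections, with no added patients, visits or data. The one downside is a small loss of efficiency if the differences turn out to be heavy-tailed.

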For financial reasons, both for the patient and for society, the government promotes the development of generic drugs at a lower cost and encourages pharmacists to make transition with patients. Many patients using the original Travoprost (Travatan Z) have their treatment modified with generic Travoprost, often without the consent of their treating physician. In Canada, a generic ophthalmic drop with the same active ingredient, at the same concentration as the reference drug, is presumed to be bioequivalent, without the need for a comparative efficacy study. [3]. It is known that Latanoprost, another prostaglandin analogue, may be less stable in generic form than in its original version (Xalatan) under certain conditions. Variations in the concentration of Latanoprost and certain physicochemical properties, such as pH , the material of the container, the size of the drop distributed, are possible which can influence the bioavailability and therefore the effectiveness of the drug [4] [5] [6]. Finally, a variation of the non-medicinal ingredients between the 2 drugs may result in a difference in the type and frequency of the adverse effects, and even affect the efficacy of the product.

In terms of therapeutic efficacy and safety of care, and for reasons of health care costs, it is important to demonstrate whether there is a therapeutic equivalence between generic Travoprost and the brand Travoprost (Travatan Z).

Is this a pilot study? yes no

1a. Review of the literature

Currently, there are many controversies in the literature on the therapeutic equivalence of anti-glaucoma drops and the opinion among experts differ.

Ophthalmic drop may not be as effective as the reference drug, as the efficacy of the generic drug does not need to be proven for market entry in Canada [3].

IOP may be less well controlled with generic Latanoprost, due to variations in the physicochemical properties of the solution, including Latanoprost concentration. These variations are due, among other things, to the properties of the bottle used or the non-medicinal ingredients that differ from the reference medicine [4][5][6][7].

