A 2007 study by Narayanaswamy et al. demonstrated a difference between the generic and original versions of Latanoprost. This pilot study involving 30 patients in a single center in India seemed to demonstrate that generic Latanoprost was less effective than Xalatan in lowering IOP. [8]. However, this is only a small study and some questions about the reliability of the results have surfaced, including concerns regarding the improper storage of the generic Latanoprost used.

On the other hand, several studies have shown an equivalence between the generic drug and the original. A randomized, double-blind study in 2011 by Diguini et al., involving 184 patients, demonstrated the non-inferiority of a generic version of Latanoprost compared to Xalatan.[9]. On the other hand, the generic version used in this study had a composition qualitatively and quantitatively identical to Xalatan, which is often not the case [4][10]. Another randomized multicentre study, by Allaire et al., included 266 patients with diagnosis of primary open angle glaucoma and ocular hypertension. Each patient was assigned to the generic Latanoprost group or the Xalatan group in a ratio of 1: 1. This study demonstrated therapeutic equivalence as well as the same safety profile [11]. Finally, a randomized crossover study by Golan et al. in 2015, compared Glautan, a generic version of Latanoprost, to Xalatan in 19 patients. The hypotensive effect and ocular side effect profile was comparable [12].

2. Objectives

The primary goal was to determine if generic Sandoz-Travoprost is as effective as brand Travatan Z in lowering intraocular pressure, as measured using Goldmann applanation tonometry.

The secondary goal was to determine if patients tolerate generic Sandoz-Travoprost as well as brand Travatan Z, using a questionnaire.

3. Methodology

a. Study Design

Randomized controlled clinical trial, unblinded, crossover trial.

The crossover design was chosen to achieve the power required all the while limiting the number of patients required.

This study was not blinded to reproduce as much as possible the real situation experienced in clinic by the patients and the doctors. The use of masked bottles by the pharmacy was considered. However, some studies have suggested that the different characteristics of drop bottles may have an impact on the size of the drop or the concentration of the drug after 30 days[14]. So it was decided to use the original bottles.

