b. Information on the medication used in the study [15]

The two drugs in the study are the original Travoprost (Travatan Z) and the generic Travoprost. Both are approved in Canada for hypotensive therapy in patients with GPAO or HTO. They are available in solution in 5 mL bottles. Since there are several companies that produce generic Travoprost, we would choose a version that will be the same for the entire study.

i. Mechanism of action:

Selective FP prostanoid receptor agonist that decreases intraocular pressure by increasing uveoscleral drainage.

ii. Posology and administration:

The recommended dosage is a drop in the affected eye or eyes once a day. The optimal effect is obtained by administering it in the evening. The instillation rate of Travatan Z ophthalmic solution (Travoprost) should not exceed 1 time / day, as it has been demonstrated that a higher frequency may decrease the reducing effect of intraocular pressure.

The reduction in intraocular pressure begins approximately 2 hours after instillation and reaches its maximum after 12 hours.

Storage between 2 ° C and 25 ° C recommended for stability.

iii. Ingredients:

Active ingredient: Travoprost 0.040mg/mL

Other ingredients: Sofzia (preservation system with boric acid, propylene glycol, sorbitol, zinc chloride), polyoxyethylenated hydrogenated castor oil 40 and purified water. A very small amount of hydrochloric acid or sodium hydroxide is added to maintain the pH at the appropriate value.

iv. Ocular adverse effects

> 10% :

Changes affecting eyelashes such as increased eyelash length and increased eyelash thickness (61%), ocular hyperaemia (30-50%)

1% to 10% :

Decreased visual acuity (5% to 10%), ocular discomfort (5% to 10%), eye pain (5% to 10%), eye pruritus (5% to 10%), blepharitis (1% to 4%), impaired vision (1% to 4%), cataracts (1% to 4%), conjunctivitis (1% to 4%), corneal staining (1% to 4%), crusting eyelids (1% to 4%), dry eye syndrome (1% to 4%), eyelid hyperpigmentation (periorbital, 1% to 4%), hyperpigmentation of the iris (1% to 4%), keratitis (1% to 4%), tearing (1% to 4%), ophthalmic inflammation (1% to 4%), photophobia (1% to 4%), subconjunctival hemorrhage (1% to 4%)

Post-marketing and / or case reports :

Bacterial keratitis (due to contamination of solution), corneal edema, cystoid macular edema, iritis, macular edema

v. Systemic adverse effects

> 10% :

None reported

1% to 10% :

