- Use of other hypotensive ophthalmic drops (except for Travatan Z or generic Travoprost)
- Use of corticosteroid
- To be pregnant
- Breast-feed
- Being monocular
- Have had glaucoma surgery such as trabeculectomy and Tube implants (eg Baerveldt, Ahmed). Patients who have had selective laser trabeculoplasty will also be excluded.
- Active intraocular inflammation
- Ocular surface disease that may interfere with an accurate measurement of IOP
- Any clinically significant eye disease that may interfere with the study

6. Recruitment

The subjects will be adult patients seen in the outpatient ophthalmology clinic of the Hotel-Dieu de Sherbrooke, who require or already use a pharmacological treatment of Travoprost original (Travatan Z) or generic Travoprost and meeting the eligibility criteria.

The subjects will be recruited at the outpatient ophthalmology clinic of the Hôtel-Dieu de Sherbrooke after a new consultation or a follow-up appointment. The physician resident will present the study to the patient, complete the consent form and obtain their signature.

The randomization will be done beforehand.

The only inconveniences for patients, no matter what group they are in, are the 2 follow-up visits, one to 3 weeks and one to 6 weeks.

7. Variables and data collection

Variable	Type	Method of measurement
age	continuous	From the chart
sex	dichotomous	From the chart

ethnic group	categorical	From the chart
diagnostic	categorical	From the chart
IOP	continuous	Goldmann applanation tonometry
initial treatment	dichotomous	From the chart
MD (visual fields)	continuous	Visual field; at the initial appointment
side effects	dichotomous	questionnaire; at the 3 week and 6 week appointments
treatment adherence (number of days missed)	continuous	questionnaire; at the 3 week and 6 week appointments

The data will be collected by the resident in charge of the project, who will be responsible for their management. Registration will be in accordance with the accepted standards of confidentiality as described in the Act respecting health services and social services.

We will use the Goldmann tonometer, a device on the slit lamp, to measure intraocular pressure. Currently, she is the gold standard for measuring intraocular pressure[13].

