The questionnaire given to patients will be a home-based questionnaire designed to check whether patients have had difficulty putting the drops, if they forget to put them on and if they have had adverse effects. The questionnaire will contain a list of side effects that patients can easily identify. The questionnaire will be filled verbally with the patient, and not just read and checked.

The mean deflection index (MD), a parameter given by the automated visual field, is an accepted measure in the literature for stratifying the glaucoma stage, either mild, moderate, or advanced [13].

8. Study Protocol

a. For patients who are new consultations:

At the first visit, the patient's sociodemographic data will be collected and a complete ophthalmic examination will be performed. This examination will include visual acuity, external examination, evaluation of the cornea, anterior chamber, iris, lens, vitreous, retina and optic nerve (with pharmacological dilatation). Intraocular pressure, gonioscopy, pachymetry and visual field Humphrey SITA fast 24-2. If the patient qualifies for the study, resident [name] will present the study. If the patient agrees, resident [name] will complete the consent form with the patient and get his signature. The patient will receive a bottle of original Travoprost (Travatan Z) or generic Travoprost according to the prior randomization. The patient will receive explanations on how to apply the drops.

During the second visit, at 3 weeks +/- 3 days, the IOP will be taken by resident [name] at 9:00 +/- 1h. A bottle of the other medicine will be given to him.

At the third visit at 6 weeks +/- 3 days, the IOP will be taken by resident [name] at 9:00 +/- 1h. The patient will have completed the study and a prescription from Travoprost will be given.

A questionnaire on tolerance and comfort of drops will be completed with the patient at the second and third visit.

b. For patients who were already followed and treated with brand Travoprost (Travatan Z) or generic Travoprost:

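### The secondary goal is to show that the generic is tolerated no worse than the brand, but section 9d plans only a McNemar difference test per side effect, with no paired difference, interval or margin, so a non-significant result cannot support it

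*Combined protocol and SAP*

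**What the plan says.** Section 2 (Objectives): "The secondary goal was to determine if patients tolerate generic Sandoz-Travoprost as well as brand Travatan Z, using a questionnaire". The background section, before 1a, gives a reason to look: differing non-medicinal ingredients "may result in a difference in the type and frequency of the adverse effects".

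Section 7 codes side effects as dichotomous, collected by "questionnaire; at the 3 week and 6 week appointments", and adds that "The questionnaire will contain a list of side effects that patients can easily identify". The list itself and its length are not given.

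Section 9d is the whole analysis plan for side effects: "A McNeman test will be used to see if each side effect is as common with both treatments".

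Section 5 gives the basis of the 69 patients (76 with allowance for loss): "The calculation of the sample size is based on a paired t test, assuming a normal distribution of intraocular pressure". No size or power is given for tolerability. Nowhere do the documents state a paired risk difference, a confidence interval, a margin or a named key side effect.

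**The concern.** The goal has the form of an equivalence or non-inferiority question. McNemar's null hypothesis is that the two rates are equal. Rejecting it shows a difference; not rejecting it leaves open every difference that the data could not exclude. Section 9d nevertheless presents the test as the means of learning whether each effect is equally common, and no other rule is offered. Followed as written, the plan can answer its secondary goal favourably only by treating non-significance as equality.

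At stake is a statement to patients that the generic is as well tolerated, made from data that might be compatible with a sizeable excess of side effects.

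**Working it through.** **The plan's own figure.** The 69 reproduces as a one-sided 0.05 paired t test for 1.5 mmHg with an SD of the difference of 3.5 × √2 = 4.95 mmHg (power 80.2%). Taking 3.5 mmHg as the SD of the difference gives 36 (one-sided) or 45 (two-sided). 69 × 1.1 = 75.9, hence 76. On either reading this is an IOP calculation and says nothing about side effects. I use 69 pairs, the expected completers.

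**Inputs for tolerability.** Section 3b.iv lists ocular effects at 1-4%, 5-10%, 30-50% (hyperaemia) and 61% (eyelash changes). Rates at 3 weeks and the within-patient correlation φ are not in the documents. Both are assumed: brand rates of 5% to 50% and φ from 0 to 0.7. The 20% row below matches no listed ocular effect and only fills the gap.

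**Power of McNemar's test.** Let pB and pG be the two risks.

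- Both products: p11 = pB·pG + φ·√[pB(1−pB)pG(1−pG)], capped at the smaller of pB and pG (the cap applies at φ = 0.7 in the 5% and 10% rows).
- Generic only: g = pG − p11. Brand only: b = pB − p11.
- Discordant pairs: M ~ Bin(69, g+b). Given M = m, generic-only pairs ~ Bin(m, g/(g+b)).
- Exact two-sided p = 2·P[Bin(m, ½) ≤ smaller count], at most 1. Power is the total probability of outcomes with p < 0.05.

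For example, at 30% vs 40% and φ = 0: p11 = 0.12, g = 0.28, b = 0.18, about 69 × 0.46 = 31.7 discordant pairs, power 17.6%.

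| Brand vs generic | φ = 0 | φ = 0.3 | φ = 0.5 | φ = 0.7 |
|---|---|---|---|---|
| 5% vs 10% | 12% | 13% | 14% | 13% |
| 5% vs 15% | 39% | 52% | 66% | 70% |
| 10% vs 20% | 29% | 39% | 51% | 70% |
| 20% vs 30% | 20% | 28% | 37% | 58% |
| 30% vs 40% | 18% | 24% | 32% | 49% |
| 50% vs 60% | 17% | 22% | 30% | 46% |

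For a 5-point excess, power is 6-14% at every rate examined.

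**One possible result.** 14 patients with an effect on the generic only and 6 on the brand only:

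- p = 2·P[Bin(20, ½) ≤ 6] = 0.115.
- Difference = 8/69 = 11.6 points.
- SE = √(20 − 8²/69)/69 = 0.0633.
- 95% CI = 11.6 ± 12.4, that is −0.8 to 24.0 points.

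The test is non-significant, yet the interval reaches 24 points against the generic.

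**What an interval would deliver.** At equal rates p, g+b = 2p(1−p)(1−φ) and the half-width is 1.96·√[(g+b)/69]. For φ from 0 to 0.7 this is 7.3 to 4.0 points at 5%, 10.0 to 5.5 at 10%, 15.3 to 8.4 at 30%, and 16.7 to 9.1 at 50%.

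**The two decision rules compared.** Take an illustrative limit of 10 points (the documents give none), a true 30% vs 40%, and φ of 0 to 0.3. Reading p>0.05 as equal tolerability would give that verdict in 76-82% of trials. Requiring the upper 95% Wald limit to lie below 10 points, enumerated over the same outcomes, would give it in about 3%.

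**The case against.** Several points on the other side stand.

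- **The plan never says that p>0.05 means equal tolerability.** A reader might infer that this misreading is planned. It is not written anywhere; the defect is that no other rule is supplied.
- **Sizing a trial on its primary endpoint is normal.** That 69 comes from IOP is not a fault in itself. It only explains why precision for side effects was never examined.
- **Low power is not universal.** A reader might infer that the trial would usually miss a 10-point excess. The calculations do not support that as a general statement: for 5% vs 15% power is 39-70%, and at φ = 0.7 it reaches 70% for 10% vs 20% and 58% for 20% vs 30%. Most ocular effects listed in section 3b.iv lie at 10% or below. High correlation is plausible, since the same patient takes the same active ingredient twice.
- **The exact test is an assumption.** The plan does not name a version. The uncorrected chi-square form has more power: 22-61% for a 10-point excess at rates of 30-50%.
- **The endpoint is secondary.** The prescribing consequence in section 12 rests on efficacy.

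None of this supplies a way to conclude equal tolerability. That gap does not depend on the assumed rates, the correlation or the version of the test.

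**Conclusion.** The point holds. The secondary goal has no analysis that can answer it in the affirmative: a non-significant McNemar test cannot show that the generic is tolerated as well as the brand, at 69 pairs or any other number.

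The size of the practical problem depends on the effect. At rates of 30-50%, a real 10-point excess would be non-significant in about half to four-fifths of trials (51-83%). At 5-10%, it would be detected in 29-70% of trials, in the upper part of that range when correlation is high. A 5-point excess would be missed in most trials at any rate examined. These figures rest on assumed 3-week rates, φ of 0 to 0.7, 69 completing pairs and the exact test.

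Because the goal is secondary and can be repaired by wording, this is a change that should be made. It ranks below any equivalent problem in the IOP analysis.

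**What to change.** **In section 9d:**

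1. Keep the yes/no coding. For each side effect report the risk on each product and the paired risk difference (generic minus brand) with a 95% CI, adjusted for period. One way is to score each patient +1 (generic only), −1 (brand only) or 0, and average the two sequence means with equal weight.
2. Use a paired score interval when discordant pairs are few. With none, the simple interval has zero width, while the score interval is ±5.3 points.
3. Keep McNemar's test as supportive, and state that p>0.05 will not be read as equal tolerability.
4. Have the investigators name the key side effects and the difference they regard as important before any outcome data are seen. The trial is unblinded (section 3a) and the resident who collects the data also manages it (section 7), so fixing these merely before analysis is too late.
5. Claim equal tolerability only for effects whose upper 95% limit is below that difference. Report the rest as estimates with their precision.
6. State that the other bottle is handed over at visit 2 with no washout described (section 8). Persistent effects, such as eyelash changes, can carry over and pull the paired difference towards zero. Period adjustment does not remove this, so no claim of equal tolerability should be made for such effects from the paired analysis alone.

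**Cost.** Wording and a little analysis; no new data, visits or patients. "Statistical calculations will be done with SPSS v20", which can run the adjusted estimate, and a spreadsheet can handle the score interval. Period adjustment costs little precision (half-width 13.5 against 13.3 points at 20% rates, φ = 0).

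The real downside is that a true claim may not be reachable. With an illustrative 10-point limit, truly equal rates, φ of 0 to 0.5 and a simple Wald limit, the claim would succeed in about 80-95% of trials at a 5% rate, 54-81% at 10%, 26-47% at 30% and 22-40% at 50%. The rule works well for uncommon effects; for common ones the result will often be descriptive only.
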